#### **1.1.2 Secondary Objectives**

To describe the following in this study population:

- Safety and tolerability of once-weekly KRDI
- Minimal residual disease (MRD) after 4 cycles, at completion of consolidation (post-transplant) or induction (transplant-deferred) and at 24 months
- Complete response (CR + stringent CR) rate after 6 cycles in patients who undergo transplant, after 8 treatment cycles in transplant-deferred patients, and at 24 months for all patients- Overall response rate (ORR)
- Progression free survival (PFS)
- Overall survival (OS)
- Quality of life (QOL)

Exploratory

- Change in body composition
- PFS by MRD status

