**Table 14: Schedule of Assessments**

Table 14A: KRDI with Autologous Stem Cell Transplant

	Screening (Within 28 days prior to registration) 	Induction Phase				Maintenance Phase (Cycles 7+)	At treatment discontinuation (30 [d ± 7] days after last dose)	Follow up  (Every 12 ± 3 weeks)
		Treatment Phase (Cycles 1-2)	Treatment Phase (Cycles 3-4)	Auto-SCT	Consolidation Phase (Cycles 5-6)			
Procedures (± 8-day window for obtaining all assessments)								
Informed consent 								
Demographics/Medical History	X							X
ECOG Performance Status	X	X	X		X	X	X	X
12 lead ECG	X							
Physical Examination including height and weight 	X	X	X		X	X	X	X
Vital Signs (temperature, heart rate, blood pressure) 	X	X	X		X	X	X	X
AE evaluation		X	X		X	X	X	
Blood type/indirect antiglobulin test	X							
Pulmonary Function Test FEV1 	X							
Bone Marrow Biopsy 	X	After 4 cycles, at the completion of consolidation, and after 24 cycles (± 3 weeks) if sCR or CR maintained (including subjects with VGPR or better and suspected isatuximab interference)					X 	
Laboratory Assessments								
CBC with diff 	X	D1, 8, 15, 22	D1, 15		D1, 15	X	X	X
Serum Chemistries 	X	D1, 8, 15, 22	D1, 15		D1, 15	X	X	X
Creatinine Clearance 	X	D1, 8, 15, 22	D1, 15		D1, 15	X	X	
SPEP, IFE, B2M	X	X	X		X	X	X	X
Free light chain testing	X	X	X		X	X	X	X
UPEP 	X	X	X 		X 	X 	X 	X 
24-hour urine, protein, creatinine 	X	X	X 		X 	X 	X 	
Pregnancy Test 	X	X	X		X	X	X	
Interference Testing 	X	X	X		X	X	X	
MRD (aspirate) 		After 4 cycles, at completion of consolidation, and after 24 cycles (± 3 weeks) if sCR or CR maintained (including subjects with VGPR or better and suspected isatuximab interference)						
Imaging Assessments								

Skeletal Survey 	X							
Extramedullary Plasmacytoma 	X							
DXA 	X					X		
Quality of Life Assessments								
EORTC-QLQ-C30		X	X		X	X	X	
EORTC-QLQ-MY20		X	X		X	X	X	

Table 14B: KRDI with Transplant-Deferred

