 Informed consent must be obtained before any study assessments are performed unless it is standard of care.

 Physical examination: A routine physical examination by the investigator (or the designated physician will include height (screening only) and weight. Height will be measured only once at screening. Weight will be measured on every visit day. Actual weight on C1D1 should be used for initial dose calculation. If a subject's weight changes by more than 10% from C1D1, the dose of all study treatments should be re-calculated.

 Vital signs (temperature, pulse/heart rate, respiratory rate, and blood pressure) will be measured in sitting position. For all infusions except C1D1 (see note below), these should be measured immediately before the start of isatuximab infusion, prior to each infusion rate increase, and at the end of isatuximab infusion.

 Pulmonary function testing (spirometry) is required only for subjects with chronic obstructive pulmonary disease or asthma. FEV1 should be measured.

 Bone marrow biopsy and aspirate for morphology, immunohistochemistry, or immunofluorescence, cytogenetics- Fluorescent in situ hybridization (FISH), and karyotype. FISH testing to include del(17p), t(4;14), t(14;16), t(14;20), and 1q duplication. Bone marrow biopsy is recommended at the time of best response for confirmation of complete response.

 Bone marrow biopsy recommended at time of progression.

 CBC with differential: Complete blood count with differential (includes white blood cells, red blood cells, platelets, ANC, lymphocyte and hemoglobin).

 Serum chemistries: To include sodium, potassium, chloride, bicarbonate, calcium, magnesium, phosphorus, blood urea, nitrogen, creatinine, glucose, albumin, total protein, alkaline phosphatase, total bilirubin, aspartate aminotransferase, alanine aminotransferase, lactate dehydrogenase, and uric acid.

 Creatinine clearance: Estimated glomerular filtration rate will be calculated using Cockcroft-Gault equation.

 Pregnancy test will be done at screening and once every cycle. Urine or serum HCG may be tested based on institutional preference.

 For all patients with VGPR, a positive serum IFE, and a negative SPEP and/or patients with an M-protein of  $\leq 0.02$  g/dL on SPEP and IgG kappa MM

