## 9.2 Minimal Residual Disease Assessment

Minimal residual disease (MRD) assessment will be assessed by next generation sequencing in both blood and bone marrow aspirate whenever a bone marrow (BM) sample is obtained as described in (Table 16) at the time points mentioned in and the Schedule of Assessments. Please see the Appendix F for details of MRD collection and processing.

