Secondary Analysis: Secondary analyses will evaluate overall response rate, MRD rate, PFS and OS. Overall response rate will be percent of patients who achieve at least partial response (PR). Percent of patients achieving MR or better will also be collected as clinical benefit response. MRD rate after 4 cycles, at completion of induction, and at 24 months will be determined by deep sequencing of genomic deoxyribonucleic acid from bone marrow samples using rearranged Ig locus-specific primers (Adaptive, Seattle, WA). PFS will be defined as the time from first dose of study treatment to the first documentation of PD or death from any cause during study. OS will be defined as the time from first dose of study treatment to death from any cause. For responders, time to response (TTR) and duration of response (DOR) will be analyzed. TTR will be defined as the time from first dose of study treatment to the first documentation of response (either PR, very good partial response (VGPR) or CR, nCR, and sCR). DOR will be defined as the time from the first PR, VGPR, or CR to the first documentation of PD or death, whichever occurs earlier.

Response rates together with confidence intervals (CIs) will be provided. Kaplan-Meier curves will be used to characterize the time-to-event outcomes (PFS, OS, response duration) when there is censoring; univariate summary statistics will be provided for TTR. In addition, outcomes including median PFS and median OS will be calculated within sub-groups based on risk status (standard vs high) and MRD status (positive vs negative).

A 90% CI for the response rate will be constructed for evaluating the efficacy of KRDI. Kaplan-Meier curves will be constructed to characterize PFS, OS, and DOR. One sample standard inferences for PFS, OS, and DOR will be made accordingly.

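### PFS and OS by MRD status are timed from first dose, although MRD response is known only from about cycle 4, with no landmark, no named grouping assessment and no place for untested patients

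*Combined protocol and SAP*

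**What the plan says.** Section 12.1 (Secondary Analysis) fixes the time origin: "PFS will be defined as the time from first dose of study treatment to the first documentation of PD or death", and "OS will be defined as the time from first dose of study treatment to death from any cause". The same section plans the subgroup summaries: "median PFS and median OS will be calculated within sub-groups based on risk status (standard vs high) and MRD status (positive vs negative").

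It lists three MRD times without tying any of them to the subgroup analysis: "MRD rate after 4 cycles, at completion of induction, and at 24 months will be determined by deep sequencing". Appendix F places the second sample after cycle 6 for transplanted patients and after cycle 8 for those deferring transplant. The last sample is conditional. Tables 14A and 14B schedule it "after 24 cycles (± 3 weeks) if sCR or CR maintained (including subjects with VGPR or better and suspected isatuximab interference"). The screening aspirate is a pre-treatment sample and gives no response status.

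Section 1.1.2 lists "PFS by MRD status" as exploratory, again without an assessment time. OS by MRD is not among the objectives.

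The last MRD time point has two definitions. It is 24 months in Section 1.1.2, Section 12.1 and the text of Appendix F. It is 24 cycles in Tables 14A and 14B and footnote 13, and C24 in the Appendix F table and shipping instructions.

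**The concern.** MRD status is a post-baseline result. Progression is a reason to stop protocol therapy (Section 5.5), so a patient normally has to stay event-free until sampling to receive a scheduled on-treatment result. If the clock still starts at first dose, the time before sampling is event-free by construction for everyone who is grouped. The resulting curve is not PFS from first dose for any group that could be identified at first dose.

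Who carries that time depends on choices the plan leaves open. If only tested patients are grouped, both groups carry it and both look better than the whole trial. If patients without a result are put in the positive group, only the negative group carries it, and an MRD-negative advantage can appear when MRD has no prognostic value. Grouping by negativity at any time has a similar effect, because patients who stay event-free longer have more chances to test negative. An analyst could follow Section 12.1 literally and choose among these after seeing the data.

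**Working it through.** **The plan's own figures.** The plan gives no number for PFS or OS by MRD. Its one design calculation reproduces: with reference rate 0.27 and alternative 0.43, rejecting at 19 of 50 gives exact power 0.804 and alpha 0.059; rejecting at 17 of 45 gives 0.804 and 0.075. Nothing below touches that test.

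**Sampling times.** Cycles are 28 days (Section 5.1); a month is taken as 30.44 days.
- After cycle 4: 4 × 28 = 112 days = 3.7 months. The ±8-day window (Section 8) allows about day 104.
- After cycle 8: 224 days = 7.4 months.
- 24 cycles: 672 days = 22.1 months, before any transplant break or delay, against 24.0 for 24 months.

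**Assumptions, not in the documents.** No true MRD effect; exponential PFS with median m of 36 to 84 months; PFS follow-up cut at T = 60 months; a share p of patients event-free at sampling is MRD-negative. Write λ = ln 2 / m and S(t) = exp(−λt).

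**Reading A: one scheduled assessment at time L, tested patients only.** Each group's curve is S(t − L) instead of S(t), so there is no gap and the median moves by L. 24-month PFS with cycle-4 grouping:
- m = 36: S(24 − 3.68) = 0.676 against S(24) = 0.630, a difference of 4.6 points.
- m = 84: 0.846 against 0.820, a difference of 2.5 points before rounding.

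With cycle-8 grouping the excess is 5.1 to 9.6 points. With a sample at 24 months, 24-month PFS is 100% by construction. For OS, assuming 5-year OS of 70% to 90% and conditioning only on being alive at cycle 4, 60-month OS is too high by 1.5 to 0.6 points.

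**Reading B: untested patients counted as positive, N = 50.**
- Negative group: events e₁ = Np[S(L) − S(T)]; person-time Np[L·S(L) + (S(L) − S(T))/λ].
- Positive group: total events N[1 − S(T)] and total person-time N[1 − S(T)]/λ, less the negative group's.
- SE of the log rate ratio: √(1/e₁ + 1/e₂), where e₂ is the number of events in the positive group.

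Example (cycle 4, m = 36, p = 0.5): (15.4/886.3) ÷ (18.8/892.6) = 0.82; SE = √(1/15.4 + 1/18.8) = 0.34; |ln 0.82| is about 0.6 SE.

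| Sample | p | Rate ratio, m = 36 to 84 | Distance from 1 |
|---|---|---|---|
| Cycle 4 | 0.5 | 0.82 to 0.86 | 0.6 to 0.3 SE |
| Cycle 8 | 0.5 | 0.69 to 0.75 | 1.0 to 0.6 SE |
| 24 months | 0.5 | 0.38 to 0.40 | 2.4 to 1.8 SE |
| 24 months | 0.2 to 0.3 | 0.44 to 0.51 | 0.9 to 1.6 SE |

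The last row matters because the last sample is taken only if response is maintained, so many event-free patients may have no result.

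**Reading C: negative at any time.** Simulation with m = 48 and tests at cycle 4, cycle 8 and 24 months while event-free:
- Status fixed at cycle 4: medians 52 and 52 months, hazard ratio 1.00.
- 30% negative at cycle 4 and 10% converting at each later test: 55 against 49 months, 0.88.
- The same with 20% converting: 56 against 46 months, 0.79.

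**Does a landmark remove the artefact?** With m = 48, no MRD effect and the clock started at cycle 4, the simulated medians are 47.9 and 48.0 months. Without the landmark both are 51.6.

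**The case against.** The strongest reply is that the natural reading of positive versus negative is tested patients at one scheduled assessment. On that reading there is no between-group bias, and the cycle-4 shift is modest. That stands. A reader might infer that the plan builds in a false MRD-negative advantage; the documents do not say so. They only fail to exclude the readings that would produce one. For the same reason, guaranteed time in both groups is a property of the tested-only reading, not of every reading.

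A reader might also infer that marrow taken at progression will be used to label patients positive. Section 9.2 describes testing by "next generation sequencing in both blood and bone marrow aspirate whenever a bone marrow (BM) sample is obtained", but that sentence goes on to tie testing to Table 16 and the Schedule of Assessments. What remains is one cell: the MRD row of Table 14B at treatment discontinuation, with a footnote reading "Bone marrow biopsy recommended at time of progression". Table 14A has no matching mark in its MRD row, and Section 12.1 lists only the three planned times. This is a weak possibility, worth one sentence to exclude.

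The ratio of 0.38 to 0.40 at the last sample should not be used as a headline. It assumes that half of all event-free patients are tested negative, which sits badly with the response condition on that sample. The OS shift given above conditions only on survival, although sampling normally also requires being on therapy. The 60-month PFS cut is an assumption: the five years in Section 5.6 concern survival contact after progression or new therapy.

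Finally, the two definitions of the last time point are a separate inconsistency that also affects the MRD rate. It is raised here because it must be settled before a late landmark can be set.

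**Conclusion.** The concern holds in limited form. As written, Section 12.1 yields MRD subgroup curves whose early part is event-free by construction in at least one group, and the plan does not settle which.

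- Tested patients only: no false gap, but about 3.7 months of guaranteed time with cycle-4 grouping, and more with later samples.
- Untested counted as positive: a false advantage of at most about 1 SE at cycle 4 or cycle 8 with 50% negative. At the last sample it is 0.9 to 2.4 SE, depending on the share tested negative.
- Ever-negative grouping: a false advantage that grows with the rate of later conversion.

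These sizes rest on the assumed exponential PFS, medians, negative shares and 60-month cut. That MRD is post-baseline and that no landmark is set do not depend on those assumptions.

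This is a cheap improvement of low priority. The summaries are descriptive and no between-group test is planned. The documents give no support for inferring that the CR conclusion or the sample size is at risk.

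**What to change.** Add one paragraph to Section 12.1:

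- Make the post-cycle-4 MRD result the main grouping.
- Analyse PFS and OS from one fixed landmark day, stated in advance, after that assessment. Include patients alive and progression-free on that day (for OS: alive).
- Classify by the sample collected on or before the landmark, using the collection date, since shipment and reporting come later.
- Do not use samples taken at progression to assign the group.
- Report landmark patients without a result as a separate group, with counts. This includes those sampled later after a longer agreed delay (Section 6.1).
- Keep the baseline risk-status subgroups timed from first dose.
- Use the last MRD time point only as a supporting landmark, after 24 months and 24 cycles are reconciled.

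Day 183 is one example of a landmark: 112 + 3 × 21 (one maximum three-week hold before each of cycles 2, 3 and 4, Section 5.2) + 8 (window, Section 8). An earlier day is acceptable; it keeps more patients but leaves more of them without a result.

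No new samples, visits or patients are needed. The cost is that patients with an event before the landmark leave this comparison. At day 183 (6.01 months) that is 50 × [1 − exp(−ln 2 × 6.01/m)], or 5.5 of 50 at m = 36 and 2.4 at m = 84, so about 2 to 6 patients.

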#### Demographic, Disposition, Study Medication:

The baseline (C1D1) characteristics of patients enrolled in the study will be summarized. An accounting will be made of the study course for all patients who received study drug and, in particular, the number of patients who died or withdrew during treatment will be specified and reasons for withdrawal categorized. Study drug administration and information on dose reductions will be summarized.

#### Safety Analysis:

Safety data will be summarized when all patients have completed the first 28-day cycle (C1). Safety data for patients undergoing SCT, as well as for patients who continued treatment without SCT, will be analyzed when all patients have completed consolidation therapy. All patients who received at least one dose of study drug will be included in the safety analyses. SAEs, treatment-

emergent AEs, vital sign measurements, clinical laboratory information, and concomitant medications will be tabulated and summarized when appropriate. Patient incidence rates of all AEs (including serious, Grade 3/4, treatment-related, and events requiring the discontinuation of investigational product), will be tabulated by system organ class (SOC), preferred term, and severity using Medical Dictionary for Regulatory Activities (MedDRA) terms and NCI CTCAE Version 5.0 severity grades. Death, SAEs, and AEs resulting in study discontinuation will also be summarized. AEs leading to dose reduction or interruption will also be tabulated. All other measurements will be summarized using means, standard deviations, medians, minimum, and maximum. Graphical displays will be provided where useful in the interpretation of results.

#### Safety Stopping Rule:

If 3 or more of the first 10 treated patients develop a Grade  $\geq 4$  adverse event (AE) that is possibly, probably or definitely related to treatment, enrollment to the trial will be temporarily suspended so that all AE data can be examined. Additionally, once the number of treated patients exceeds 10, if at any point during treatment 30% or more of patients develop a Grade  $\geq 4$  adverse event (AE) possibly/probably/definitely related to treatment, enrollment will be temporarily suspended for review of AE data. These stopping rules apply to the cumulative number of Grade  $\geq 4$  AEs and patients treated across study arms, not within arms separately.

If 3 or more of the first 10 treated are unable to collect adequate stem cells for autologous stem cell transplant, enrollment to the trial will be temporarily suspended so that the stem cell collection data can be examined. Additionally, once the number of treated patients exceeds 10, if at any point during treatment 30% or more of patients are unable to collect adequate stem cells for autologous stem cell transplant, enrollment will be temporarily suspended for review of the stem cell collection data.

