The ARROW study provided further support for the safety and efficacy of once weekly carfilzomib dosing.[9] 478 patients were randomly assigned and included in the efficacy analyses (240 to receive once weekly carfilzomib; 238 to receive twice weekly carfilzomib). Median progression-free survival was higher in the once weekly group than the twice weekly group (11.2 months [95% CI 8.6–13.0] vs 7.6 months [5.8–9.2]; hazard ratio [HR] 0.69, 95% CI 0.54–0.83; p=0.0029). The incidence of grade 3 or worse adverse events was higher in the once weekly group than the twice weekly group (68% [n=161] vs 62% [n=145]); the most common events were anemia, pneumonia, and thrombocytopenia (42 [18%] vs 42 [18%], 24 [10%] vs 16 [7%], and 17 [7%] vs 16 [7%], respectively for once weekly carfilzomib vs twice weekly carfilzomib). A lower proportion of patients had grade 3 or worse cardiac failure in the

once weekly group (7 [3%]) than in the twice weekly group (10 [4%]). Treatment-related deaths occurred in five (2%) of 238 patients in the once weekly group (sepsis [n=1], death [n=1], acute lung injury [n=1], acute respiratory distress syndrome [n=1], and tumor lysis syndrome [n=1]) and in two (1%) of 235 patients in the twice weekly group (plasma cell myeloma [n=1] and congestive heart failure [n=1]). There were 58 deaths in the once weekly group and 68 deaths in the twice weekly group at the time of data cutoff. The once weekly dosing demonstrated superior efficacy with comparable toxicity.

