### Dose Delay and Toxicity Management

ONLY if any of the following criteria are met and the event cannot be ascribed to lenalidomide, carfilzomib, dexamethasone, or underlying MM, the isatuximab infusion must be held to allow for recovery from toxicity. The criteria for a dose delay are:

- Grade 4 hematologic toxicity (except for Grade 4 lymphopenia), or Grade 3 or higher thrombocytopenia with bleeding.
- Febrile neutropenia of any grade.
- Neutropenia with infection, of any grade.
- Grade 3 or higher nonhematologic toxicities with the following exceptions:
  - Grade 3 nausea or Grade 3 vomiting that responds to antiemetic treatment.
  - Grade 3 diarrhea that responds to antidiarrheal treatment.
  - Grade 3 fatigue or asthenia that was present at baseline and lasts for <7 days after the last administration of isatuximab.
  - Grade 3 or 4 electrolyte disturbances which can be managed with replacement therapy.

If isatuximab administration does not commence within the prespecified window (Table 8) of the scheduled administration date, then the dose will be considered a missed dose. Administration may resume at the next planned dosing date.

The maximum delay for toxicity before treatment is permanently discontinued will be 3 weeks; however, delays due to other circumstances should be discussed with the Principal Investigator. Delays of >3 weeks must be discussed with the Principal Investigator. Re-treatment will be at the discretion of the Principal Investigator.

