**Adverse Events**

**7.1 Definitions**

**Adverse Event (AE)**

An AE is any undesirable sign, symptom or medical condition or experience that develops or worsens in severity after starting the first dose of study treatment or any procedure specified in the protocol, even if the event is not considered to be related to the study.

An adverse event is any change in health occurring in a person who is a participant in biomedical research, whether this change is related or not to the research or to the product that the research is being conducted on. This includes any newly occurring event or previous condition that has increased in severity or frequency since the administration of drug.

For this protocol, an abnormal laboratory value will not be assessed as an AE unless that value leads to discontinuation or delay in treatment, dose modification, therapeutic intervention, or is considered by the investigator to be a clinically significant change from baseline.

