## **7.2 Adverse Event Recording and Reporting**

Reporting participating investigators will assess the occurrence of AEs and SAEs at all participant evaluation time points during the study. All AEs and SAEs whether reported by the participant, discovered during questioning, directly observed, or detected by physical examination, laboratory test or other means, will be recorded in the participant’s medical record and on the appropriate study-specific case report forms. All AEs must be recorded in the participant’s medical record, stating the duration and intensity of the event, action taken by the investigator and outcome of the event. The investigator must evaluate the causal relationship between the study drug(s) and the adverse event.

The investigator must evaluate all abnormal laboratory results to determine the clinical significance.

All AEs detected by the investigator or by the participant must be recorded on the appropriate study-specific CRFs, stating the duration and intensity of the event, action taken by the investigator and outcome of the event. The investigator must evaluate the causal relationship for each AE.

The descriptions and grading scales found in the CTEP Version 5.0 of the NCI Common Terminology Criteria for Adverse Events (CTCAE) will be utilized for AE reporting. The CTEP Version 5.0 of the CTCAE is identified and located on the CTEP website at:  
[http://ctep.cancer.gov/protocolDevelopment/electronic\\_applications/ctc.htm](http://ctep.cancer.gov/protocolDevelopment/electronic_applications/ctc.htm)

Each adverse event will be assessed to determine if it meets the criteria for SAE reporting. If an SAE occurs, expedited reporting will follow local policies and regulations as appropriate. Hematologic adverse events will be recorded/reported only if >grade 2 or if an action on study drug was required. These events should be captured on the adverse event pages of the CRF only.

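### The only toxicity suspension rule pools related Grade 4 and Grade 5 events under one 30% limit, with no separate boundary for related deaths and an inconsistent counting unit

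*Combined protocol and SAP*

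**What the plan says.** Section 12.1, Safety Stopping Rule, sets the first trigger with "If 3 or more of the first 10 treated patients develop a Grade" 4 or higher adverse event. The event must be "possibly, probably or definitely related to treatment, enrollment to the trial will be temporarily suspended so that all AE data can be examined". The second trigger applies "once the number of treated patients exceeds 10, if at any point during treatment 30% or more of patients develop a Grade" 4 or higher related event. The paragraph closes with "These stopping rules apply to the cumulative number of Grade" 4 or higher events and patients treated, pooled over study arms. A further rule in the same section concerns only failure to collect stem cells. No operating characteristics are given for either rule.

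Deaths also appear elsewhere. Section 7.4 requires Grade 5 events to be reported within 24 hours, section 7.5 covers expedited reporting to the FDA, and section 11.0 has the DSMC review toxicity up to four times a year, with a summary of deaths among the items it may receive. The Safety Analysis paragraph of 12.1 plans the first safety summary once all patients have completed cycle 1.

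On laboratory values, section 7.1 says "an abnormal laboratory value will not be assessed as an AE unless that value leads to discontinuation or delay in treatment, dose modification, therapeutic intervention". A change that the investigator judges clinically significant also qualifies. Section 7.2 says "Hematologic adverse events will be recorded/reported only if >grade 2 or if an action on study drug was required". The list of events of special interest in 7.1 includes Grade 4 or higher cytopenias with no condition about action. Section 6.1 lists among the criteria for an isatuximab hold "Grade 4 hematologic toxicity (except for Grade 4 lymphopenia").

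**The concern.** This is the trial's only pre-set toxicity boundary for a four-drug combination. Because a fatal and a non-fatal Grade 4 event each count once against a 30% limit, the boundary sits far above any related-death rate the protocol cites. Section 2.3 reports, for once-weekly carfilzomib, "Treatment-related deaths occurred in five (2%) of 238 patients in the once weekly group". A related-death rate several times that could run through the whole trial without the deaths themselves crossing the limit, and any response would then depend on discretion.

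Two points of wording add to this. The triggers count patients but the closing sentence speaks of a cumulative number of events, so two readers could keep different tallies. And it is not clear whether a related Grade 4 laboratory value on which nobody acted enters the tally at all.

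**Working it through.** **Inputs.** The limit is 3 of the first 10, then 30% or more of those treated, with at most 50 patients (12.1). The cited related-death rate is 5/238 = 2.1% (section 2.3). The plan gives no figure for this rule to reproduce. Its one checkable design figure, 80% power with 19 or more complete responses in 50, does reproduce (exact power 0.804, one-sided error 0.059), but it bears only on the sample size.

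**Boundary.** Suspension needs 3 patients while n ≤ 10, and the smallest integer at or above 0.3n afterwards: 4 of 11, 6 of 20, 9 of 30, 12 of 40, 15 of 50. The largest counts that do not suspend are therefore 2/10, 5/20, 8/30, 11/40 and 14/50.

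**Deaths alone.** For the first 10, P(X ≥ 3) with X ~ Bin(10, p). At p = 0.05: 1 − 0.95^10 − 10(0.05)(0.95^9) − 45(0.05²)(0.95^8) = 1 − 0.5987 − 0.3151 − 0.0746 = 0.0115. Up to 50, an exact patient-by-patient recursion removes probability whenever the count reaches the boundary. It takes each outcome as known before the next patient is counted.

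| Related-death rate | Trip within first 10 | Trip by patient 50 |
|---|---|---|
| 2% | 0.1% | 0.1% |
| 5% | 1.2% | 1.2% |
| 10% | 7.0% | 8.0% |
| 15% | 18.0% | 22.2% |
| 20% | 32.2% | 42.8% |

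Late deaths would not raise these values. An observed count can never exceed the eventual count among the same patients, so a crossing seen with delay would also be a crossing without delay.

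**Deaths plus non-fatal Grade 4 events.** With an independent background patient rate g (assumed, as the documents give no Grade 4 rate) and related-death rate d, the pooled rate is u = 1 − (1 − g)(1 − d). For example, g = 0.20 and d = 0.05 give u = 0.24. Probability of tripping by patient 50:

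| g | d = 0 | d = 5% | d = 10% |
|---|---|---|---|
| 0 | 0% | 1.2% | 8.0% |
| 10% | 8.0% | 20.5% | 38.3% |
| 20% | 42.8% | 61.1% | 77.4% |
| 30% | 83.9% | 92.1% | 96.7% |

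The rule gives 8.0% both for 10% non-fatal events with no deaths and for 10% deaths with no other events. It cannot tell the two apart.

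**Unit.** Take a 10% patient rate. Counting patients, P(3 or more in the first 10) is 7.0%. Counting events, with 1 + Poisson(1) per affected patient (mean 2, assumed), P(total ≤ 2) = 0.3487 + 0.3874 × 2e^−1 + 0.1937 × e^−2 = 0.3487 + 0.2850 + 0.0262 = 0.660, so the probability is 34.0%. The range is 7.0% at one event per affected patient to 34.0% at a mean of two.

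**Laboratory values.** Section 7.1 sets when a laboratory value becomes an adverse event; 7.2 sets which hematologic events are recorded. In 7.2, the alternative of drug action implies that events above Grade 2 are recorded without it, which strains against 7.1. Grade 4 neutropenia is not affected: Table 9 requires both drugs to be held and filgrastim added, and section 5.2 bars intra-cycle dosing on scheduled laboratory days below a neutrophil count of 500, so it is an adverse event under 7.1 as well. Lymphopenia has no row in Table 9 and is exempt from the isatuximab hold, so it is the main value left open.

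**The case against.** The strongest reply is that deaths will seldom occur alone. Two related deaths in the first 10 suspend enrollment as soon as one of the other 8 patients has a related Grade 4 event. At assumed background rates of 10%, 20% and 30%, that happens with probability 1 − 0.9^8 = 57%, 1 − 0.8^8 = 83% and 1 − 0.7^8 = 94%. This stands. A reader might infer that the rule ignores deaths altogether, and the documents do not support that: the counts of 2 in 10 and 14 in 50 hold only when nobody else has a qualifying event. What remains is that any such suspension reflects the pooled rate, and its chance depends on unrelated background toxicity.

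Second, deaths are overseen elsewhere. Sections 7.4, 7.5 and 11.0 do provide rapid reporting and committee review, so it would be wrong to say deaths go unwatched. None of them sets a count or ties one to enrollment.

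Third, a reader might infer that the protocol holds two rival definitions of an adverse event and that expected cytopenias will trip the rule. Neither follows. Sections 7.1 and 7.2 are a definition and a recording threshold in tension. The 64% lymphopenia in section 2.3 is Grade 3/4 combined, in relapsed or refractory patients, with no Grade 4 rate given. The probabilities of 8%, 43% and 84% at background rates of 10%, 20% and 30% are therefore scenarios, not forecasts.

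Fourth, both operative triggers do count patients, so reading the rule as an event count is strained. That makes the unit a wording repair, but one inside the rule itself.

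**Conclusion.** The point holds in limited form and should be fixed; it does not invalidate the design. The single toxicity rule has no boundary specific to related deaths. On deaths alone it trips by patient 50 with probability about 1% at a 5% related-death rate, 8% at 10% and 43% at 20%, against a cited 2% for once-weekly carfilzomib. These figures assume that patients are the unit, that outcomes are independent and known at once, and that no other related Grade 4 or higher event occurs. With such events the probability rises, through the pooled rate only. The closing sentence conflicts with the triggers on the unit and refers to arms in a single-arm trial. The status of a related Grade 4 laboratory value without action, mainly lymphopenia, needs to be stated; how much it matters cannot be sized from the documents.

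**What to change.** In section 12.1:

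1. Add a separate boundary for Grade 5 events at least possibly related to treatment, at a count fixed in advance with the DSMC, leading to temporary suspension of enrollment and DSMC review.
2. Define the unit as patients with at least one qualifying related event, and remove the references to a cumulative number of events and to study arms.
3. Reconcile the adverse event definition and special-interest list in 7.1 with the recording rule in 7.2, and say whether a related Grade 4 laboratory value with no action taken counts toward the rule. Keep attributed adverse events as the basis. Grades derived from blood counts carry no attribution, and substituting them would add cytopenia triggers.

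The cost is wording, with no change to dose, sample size or efficacy test, and possibly one extra short pause. For illustration only, a review at the second related death among 50 would be reached with probability 1 − 0.98^50 − 50(0.02)(0.98^49) = 26% at a 2% rate and 1 − 0.9^50 − 50(0.1)(0.9^49) = 97% at 10%. The count itself is for the DSMC and the sponsor to set.
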